# 4. STUDY POPULATION AND ENROLLMENT

#### 4.1 Setting

Intermountain Healthcare (hereafter "Intermountain") is a nonprofit health system based in Salt Lake City, Utah with 23 hospitals in Utah and Idaho. Code Sepsis implementation will occur in a teaching ED (IMC, my "home" hospital) providing 89,000 visits annually (2.8% with clinical sepsis) for an economically and ethnically diverse population of 1.1 million in Salt Lake County, Utah plus referrals

from Wyoming, Nevada, and Idaho. To avoid spillover effects, concurrent control data will be electronically abstracted from two Intermountain EDs (Utah Valley Hospital and Dixie Regional Medical Center) staffed by other physician groups (Table 1).

Table 1. Study hospital characteristics

	, ,			
Site	Description	Hospital beds	ED beds	Annual ED visits
IMC	Tertiary/teaching	472	56	89,000
Utah Valle	ey Regional referral	395	28	49,000
DRMC	Regional referral	321	35	65,000

#### 4.2 Study Population

We will study adult, non-trauma patients from the IMC ED and two control EDs during three phases (Figure 1): baseline (1 year, standard care at all sites); run-in (3 months, IMC ED launches/fine tunes the Code Sepsis protocol); and Code Sepsis implementation (1 year, Code Sepsis at IMC, standard care in control EDs). For this pre/post implementation trial, in which there will be no direct patient contact and in which we are comparing current standard care processes to a new, redesigned standard care

processes in a non-randomized fashion, all ED patients who meet inclusion and do not meet exclusion criteria will be included in the analysis.

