#### **1.2 Definitions**

- Adverse Event: Any untoward medical occurrence associated with the use of a drug or a study procedure, whether or not considered drug related.
- Adverse reaction: An adverse reaction means any adverse event caused by a study intervention. An adverse reaction is a subset of all suspected adverse reactions where there is a reason to conclude that the study intervention caused the event.
- **Door-to-antibiotic time**: Primary outcome; the time from the first recorded arrival time in ED (usually ED triage or registration) and the time the first eligible antibiotic was administered.
- **Hypotension**: SBP <90 mmHg or MAP <65 mmHg or, where applicable, receipt of vasopressor medication
- Intention to Treat (ITT): All eligible patients who present to the ED will be included in the ITT cohort for the purposes of analyzing the primary and secondary study outcomes.
- **PHI:** identifiable health information that is used, maintained, stored, or transmitted by a HIPAA-covered entity
- **SAEs:** Serious Adverse Events Adverse events that are serious and unexpected and have a reasonable possibility that the event was due to a study procedure
- Sepsis: Life-threatening organ dysfunction resulting from a dysregulated host response to infection, clinically identified in the emergency department (ED) by an acute rise in the Sequential Organ Failure Assessment (SOFA) score while in the ED ≥2 points above baseline plus suspected or confirmed infection in the ED.1
- Sepsis mimic: Clinical condition which may cause patient to exhibit and/or be treated for sepsis even though infection is not actually present. For the present study, pulmonary embolism (PE) and congestive heart failure (CHF) have been identified as sepsis mimic conditions.
- Septic shock: Sepsis associated with hypotension requiring administration of vasopressors.
- Study hospital: Defined as the hospital where the patient presented to the ED.
- **Suspected adverse reaction**: any adverse event for which there is a reasonable possibility that the study procedures caused the adverse event. Reasonable possibility means there is evidence to suggest a causal relationship between the study procedures and the adverse event. A suspected adverse reaction implies a lesser degree of certainty about causality than adverse reaction (21 CFR 312.32(a)).

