#### 3.7.2 Secondary outcomes

- Clinical/patient-centered secondary outcomes (measured among all ED sepsis patients):
  - 1) All-cause mortality to day 30
  - 2) All-cause mortality to 1 year
  - 3) In-hospital all-cause mortality
  - 4) Hospital charges: Amount charged to patient for their medical care during index ED visit and associated hospitalization.
  - 5) Hospital length of stay
- Process/feasibility secondary outcomes
  - 1) Code Sepsis activation rate: Measured as the percentage of all ED patients for whom the Code Sepsis protocol was activated.
  - 2) Code Sepsis activation accuracy metrics. Accurate Code Sepsis activation is defined as activation for patients who have sepsis while in the ED and no activation for patients who do not have sepsis in the ED.
- Adverse effects and unintended outcomes of protocol implementation

- 1) Antibiotic utilization percentage: measured as the fraction of (1) all ED patients; (2) Code Sepsis activation patients; or (3) "likely" sepsis patients who received IV or IV-equivalent antibiotics.
- 2) Antibiotic spectrum: Total Stenehjem antibiotic spectrum score for all antibiotics administered in first 24 hours, measured for (1) all ED patients or (2) sepsis patients
- 3) Antibiotic overtreatment rate: Percentage of "sepsis mimic" patients who received IV or IVequivalent antibiotics in the ED.
- 4) New onset C. difficile colitis incidence: Percentage of (1) all ED patients and (2) ED sepsis patients with a positive stool test for *Clostridium difficile* colitis between 72 hours and 90 days after ED arrival.
- 5) Adverse drug & allergic reaction incidence: Measured as the fraction of 1) all ED patients and (2) ED sepsis patients with a discharge diagnosis code consistent with anaphylaxis or with an adverse reaction to antibiotics (see Appendix C).
- Potential exploratory outcomes
  - 1) Measures of organ failure trajectory, to include change in the SOFA score between hospital day 1 and hospital day 3, and overall and organ-specific measures of organ failure-free days through day 28.

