#### 8.1.3. Risks to patients exposed to the Code Sepsis protocol

Patients presenting to the intervention hospital during phases #2 and 3 (run-in implementation and full implementation) will be exposed to and may receive care using the "Code Sepsis" version of standard care. The Code Sepsis protocol is designed to accelerate evaluation, testing, and treatments that the patient would have eventually received under now current standard care. The Code Sepsis intervention is therefore expected to pose no more than minimal risks to ED patients exposed to the protocol, including specifically sepsis patients for whom the Code Sepsis protocol is activated. The potential risks to subjects due to this protocol include:

- 1) Adverse drug reactions or antibiotic-associated infections related to unnecessary or overtreatment antibiotic treatment with prespecified regimens.
- 2) Delay in diagnosis of non-infectious problems due to focus on sepsis or infection related to Code Sepsis activation.
- 3) Delay in care related to resource allocation away from non-Code Sepsis patients without sepsis (bystanders without sepsis).
- 4) For sepsis patients for whom the Code Sepsis protocol is not activated (i.e. bystanders with sepsis), delay in care related to lower index of suspicion for sepsis leading to delayed diagnosis or resource allocation away from these patients.

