# Inclusion/exclusion criteria

Cohort	Inclusion	Exclusion	Cohort eligibility indicator variable*
ED sepsis cohort (primary analysis cohort)	
 
(1) Age ≥18 years
 
(2) Arrival to an intervention or control ED during study period
 
(3) Met all Sepsis-3 criteria in the ED
 
Acute organ failure in the ED defined by SOFA score while in the ED ,≥2 points above baseline
 
Suspected or confirmed infection while in the ED, based on having both: 
 
i. Administration of ,≥1 IV or IV-equivalent antibiotics while in the ED for suspected infection (i.e. antibiotics not given for prophylaxis)
 
ii. Collection of ,≥1 body fluid cultures while in the ED
 
 
 
	
 
Trauma patient
 
Subsequent eligible ED visit with sepsis after first eligible encounter during an analysis window
 
	cohort_sepsis
All adult ED patients cohort	
 
(1) Age ≥18 years
 
(2) Arrival to an intervention or control ED during study period
 
	
 
Trauma patient
 
Received antibiotics within 6 hours prior to study ED arrival
 
Subsequent eligible ED visit after first eligible encounter during an analysis window
 
Left ED without evaluation or treatment
 
	cohort_all
Sepsis high-risk cohort	
 
Age ≥18 years
 
Arrival to an intervention or control ED during study period
 
First recorded temperature ≥38.0°C
 
First-recorded vital sign data meets ≥2 of:         
 
a. Systolic blood pressure <90 mmHg
 
b. Glasgow Coma Scale (GCS) score <15
 
c. Respiratory rate ≥22 breaths/min or oxygen saturation <85%
 
 
 
	
 
Trauma patient
 
Received antibiotics within 6 hours prior to study ED arrival
 
Subsequent eligible ED visit after first eligible encounter during an analysis window
 
Left ED without evaluation or treatment
 
	cohort_risk

Cohort	Inclusion	Exclusion	Cohort eligibility indicator variable*
Sepsis	(1) Age ≥18 years	(1) Trauma patient	cohort_mimics
mimic	(2) Arrival to an intervention or control ED during study period	(2) Received antibiotics	

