cohort	(3) Primary ICD-10-CM discharge diagnosis code of venous thromboembolism or congestive heart failure and no ICD- 10-CM discharge diagnosis code for infection in any position	
 
within 6 hours prior to study ED arrival
 
(3) Subsequent eligible ED visit after first eligible encounter during an analysis window
 
(4) Left ED without evaluation or treatment
 
	

\* For analyses including all eligible encounters for a given cohort (i.e., ignoring exclusion criteria #3), the name of the indicator variable is appended with "\_sens" (e.g. "cohort\_sepsis\_sens")

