### Safety outcomes

	Analysis		
Outcome	cohort	Description	Outcome variable
Antibiotic utilization	All patient	Receipt of IV or equivalent antibiotics within 24	abx_24h
	cohort	hours of ED arrival	
Antibiotic utilization	Sepsis	Receipt of of receiving IV or equivalent antibiotics	abx_24h
	high-risk	within 24 hours of ED arrival	
	cohort		
Potential adverse effect	Sepsis	Antibiotic-related adverse event (a discharge	<pre>icd10_ae_summary</pre>
of antibiotics	cohort	diagnosis code consistent with anaphylaxis or	
		with an adverse reaction to antibiotics)	
Potential adverse effect	All patient	Antibiotic-related adverse event (a discharge	<pre>icd10_ae_summary</pre>
of antibiotics	cohort	diagnosis code consistent with anaphylaxis or	
		with an adverse reaction to antibiotics)	
New-onset C difficile	Sepsis	New positive stool test for Clostridium difficile	cdiff_72h_new_analysis
	cohort*	colitis between 72 hours and 90 days after ED	ineligible)
		arrival	
		* Excludes patients with a positive C. difficile	
		assay in the 14 days preceding ED arrival or	
		within 72 hours following ED arrival	

	Analysis		
Outcome	cohort	Description	Outcome variable
New-onset C difficile	All patient cohort*	New positive stool test for Clostridium difficile colitis between 72 hours and 90 days after ED arrival	cdiff_72h_new_analysis (missing if ineligible)
		* Excludes patients with a positive C. difficile assay in the 14 days preceding ED arrival or within 72 hours following ED arrival	
Antibiotic	Sepsis	Receipt of antibiotics in the ED among ED	abx_ed
overtreatment rate	mimic	patients with a primary hospital discharge	
	cohort	diagnosis of congestive heart failure or venous	
		thromboembolism	
False-positive	Sepsis	Final adjudicated infection status is "not	uninfected
presumptive infection	cohort	infected" among ED patients meeting sepsis	
diagnosis rate		criteria	

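### The SAP drops patients who left the ED unseen from the all-ED and high-risk cohorts; this post-arrival exclusion departs from the protocol, no planned analysis tests it, and it could shift the antibiotic-utilization comparison either way

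*Protocol*

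**What the plan says.** **Protocol.** Sections 2.4.3 and 4.2.3 exclude only patients under 18 and trauma patients. Section 4.2 states that "all ED patients who meet inclusion and do not meet exclusion criteria will be included in the analysis". Section 1.2 defines intention to treat by presentation: "All eligible patients who present to the ED will be included in the ITT cohort", for both primary and secondary outcomes. Section 3.7 repeats the intention-to-treat basis. Section 3.7.2 lists antibiotic utilization among the secondary outcomes, "measured as the fraction of (1) all ED patients" among other denominators.

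**SAP.** The table under Inclusion/exclusion criteria adds "Left ED without evaluation or treatment" for the all-adult-ED and high-risk cohorts, and again for the mimic cohort ("4) Left ED without evaluation or treatment"). The sepsis cohort has no such exclusion, and it already requires an ED antibiotic and a culture. Under Safety outcomes, utilization in the all-patient and high-risk cohorts is "Receipt of IV or equivalent antibiotics within 24" hours of arrival. The footnote to the cohort table defines alternative cohorts that relax only exclusion 3, the first-visit rule. The Sensitivity analyses section does not bring back patients who left unseen, and no outcome counts them.

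**The concern.** Whether a patient leaves unseen is settled after arrival and plausibly depends on waiting time. Protocol section 8.1.3 names a route by which the intervention could change it: "Delay in care related to resource allocation away from non-Code Sepsis patients without sepsis". The SAP's safety covariates include no measure of crowding or waiting.

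Patients who leave unseen are mostly untreated, so the exclusion takes mostly untreated people out of the utilization denominator. If more of them leave at the intervention ED after launch, the rate among those retained can rise although nobody extra is treated. If fewer leave, a real rise can be hidden. All-ED utilization is one of several outcomes that bear on the aim in section 3.2 of faster treatment without more overtreatment. Section 2.4 also promises to measure bystander effects, yet the patients most directly affected by delay would be removed without being counted.

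**Working it through.** **The plan's own denominator.** The four groups in protocol 4.2.1 sum to 135,000 + 100,000 + 170,000 + 125,000 = 530,000, which matches the figure of up to 530,000 in section 9.2.3. That total has no deduction for patients who left unseen.

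**Inputs not in the documents (assumptions).** Share leaving unseen at baseline, L = 3% at every ED. Antibiotic use either u = 10% per arrival, or p = 12% per evaluated patient (so u = 0.12 × 0.97 = 11.64% per arrival). Leavers untreated.

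**Formula.** The rate among retained patients is u/(1 − L). With u constant, the DID shift is the change in u/(1 − L) at the intervention ED minus the change at the control EDs.

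**A change shared by all sites.** L rises from 3% to 5% everywhere: shift 0.000 points. With unequal baselines (5% intervention, 1% control, both up 2 points, u = 10%), the shift is about 0.02 points.

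**A change at the intervention ED only, extra leavers otherwise untreated.**
- u = 10%, +1 point: 0.10/0.96 − 0.10/0.97 = 0.107 points. At +2 points, 0.217; at −2 points, −0.208.
- p = 12%, +1 point: 0.1164/0.96 − 0.12 = 0.125 points. At +2 points: 0.1164/0.95 − 0.12 = 0.253.

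**Standard error.** SE = √[rate × (1 − rate) × Σ(1/n)].
- 10%, with the four group sizes of 4.2.1: 0.168 points.
- 12%, with the annual visits in protocol Table 1 (89,000 intervention; 49,000 + 65,000 = 114,000 control) in each phase: 0.206 points.
- The same, assuming 65% of visits survive the first-visit rule: 0.206/√0.65 = 0.255 points.

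A 1-point differential change is therefore worth about 0.5 to 0.6 of an SE (0.125/0.255 = 0.49; 0.107/0.168 = 0.64). At u = 10% this raises the chance of a nominally significant DID from 5% to about 10%. A 2-point change raises it to about 25% at u = 10%, and to 17-23% at p = 12%.

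**The same change if the extra leavers would have been treated at the usual 12%.** The rate among evaluated patients stays at 12%, so the SAP's version is unbiased. The per-arrival rate moves instead: 0.12 × 0.96 − 0.12 × 0.97 = −0.12 points for a 1-point change, and −0.24 for 2 points.

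**High-risk cohort.** Assuming 90% use per arrival, and leaving rising from 1% to 2% at the intervention ED only: 0.90/0.98 − 0.90/0.99 = 0.93 points. The documents give no size for this cohort, so no SE can be set against it.

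**The case against.** Several points on the other side stand.

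- **The controls do most of the work.** The analysis is a DID with two concurrent control EDs. A reader might infer from the post-phase dates (February 2020 to February 2021) that the pandemic by itself distorts the result. It would do so only if its effect on leaving differed by site. The documents do not say that ED volume or leaving rates changed.
- **Little reach into the named overtreatment outcome.** A reader might infer that the antibiotic overtreatment rate is compromised. That outcome uses the mimic cohort, which requires a "Primary ICD-10-CM discharge diagnosis code of venous thromboembolism or congestive heart failure". A patient who was never evaluated would rarely have one.
- **High-risk cohort.** Entry needs a recorded fever and at least two abnormal first vital signs. How many such patients leave unseen is unknown.
- **Size.** Two points of 89,000 visits is 1,780 extra leavers a year. The power section's 30% of 1,650 sepsis patients is 495 activations, or about 3.6 extra leavers for each. Non-sepsis activations would lower that ratio, but their number is not given. A 2-point scenario is therefore demanding.
- **The estimand.** Use among evaluated patients is a defensible measure of prescribing, and the last calculation for the all-ED cohort shows that a per-arrival rate carries its own bias.
- **Status.** The SAP labels safety outcomes hypothesis generating.

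Together these points defeat any claim that a false signal will result, and any case for replacing the main analysis. They do not answer the mismatch with the protocol or the lack of a check. A DID cannot remove a change confined to the intervention ED, and that is the mechanism the protocol itself names.

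**Conclusion.** The SAP conditions its all-ED and high-risk utilization analyses on a post-arrival event. That conflicts with the protocol's eligibility and intention-to-treat rules, and nothing planned tests it. The all-ED DID could be shifted in either direction by about 0.11-0.13 points per 1-point differential change in leaving, against an SE of about 0.17-0.26. This rests on assumed rates (10-12% use, 3% leaving), on extra leavers who would not have been treated, and on unadjusted normal-approximation SEs. Those SEs may be too small, because the visit counts are not stated to be limited to adult, non-trauma patients, and the first-visit rule reduces them further. If the extra leavers would have been treated at the usual rate, the SAP's version is the unbiased one.

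The documents cannot show whether any differential change occurred. The mimic cohort is barely touched, and the sepsis cohort and door-to-antibiotic time not at all. This is an untested selection in a safety check, and it is cheap to examine.

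**What to change.** Keep the present analysis and make three changes.

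1. Report the proportion who left unseen by ED and phase, with the same DID model, as a bystander safety outcome. ED disposition is already among the data elements in protocol section 6.5.
2. Add a sensitivity analysis of utilization in the all-ED and high-risk cohorts that includes these arrivals.
   - Take the outcome from the recorded 24-hour antibiotic variable rather than setting it to untreated.
   - Run it on all encounters, or apply the first-visit rule so that a left-unseen visit does not displace a later evaluated one.
   - Adjust only for covariates known at registration, or use the SAP's multiple imputation. State that imputation applies here even when at least 95% of encounters are complete; otherwise the complete-case rule could drop these patients again.
3. Reconcile the SAP exclusion with the protocol's intention-to-treat definition, and give the reason for it.

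The cost is SAP wording and one or two extra analyses. The weak point is that patients who left may lack temperature, blood pressure and acute physiology score, so the added analysis leans on imputation or on thinner adjustment.

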#### 4.2.1 Exposure groups

The group within which patient is analyzed is determined by the combination of (1) when the patient presents to the ED and (2) which hospital/ED to which the patient presents (Figures 1 and 2).

A. Pre-implementation control group at non-intervention hospitals: Admission to ED at non-

Adult ED patients Pre-implementation Post-implementation Study (study phase #1) (study phase #3) phase ↘ Study Intervention ED Intervention ED Site Ł Ł ` Non-Non-Non-Non-ED Sepsis Sepsis Sepsis Sepsis sepsis sepsis diagnosis sepsis sepsis Code Sepsis Study Standard care Standard care protocol Standard care condition implemented Patient Default Default Default Default Code treatment Sepsis care care care care

Figure 2. Subject allocation by study phase and hospital

intervention hospitals (Utah Valley Hospital and Dixie Regional Medical Center) prior to Code Sepsis implementation (estimated N=135,000)

- B. Pre-implementation control group at intervention hospital: Admission to ED at IMC prior to Code Sepsis implementation (estimated N=100,000)
- C. Post-implementation control group at non-intervention hospitals: Admission to ED at nonintervention hospitals (Utah Valley Hospital and Dixie Regional Medical Center) after implementation of Code Sepsis protocol at IMC (estimated N=170,000)
- D. Exposure group: Admission to ED at IMC during full Code Sepsis implementation (estimated N=125,000)

#### 4.2.2 Inclusion criteria:

- ED patient at Intermountain Medical Center, Utah Valley Hospital, Dixie Regional Medical Center
- ED arrival beginning 1 year prior to date of Code Sepsis implementation at Intermountain Medical Center and continuing through 15 months after Code Sepsis implementation date.
- Age ≥18 years

#### 4.2.3 Exclusion criteria:

- Age <18 years
- Trauma patient

#### 4.2.4 Inclusion/exclusion criteria rationale

Patients <18 years of age are excluded because the mechanisms, manifestations, and management of sepsis in children <18 years of age are often distinct from those applicable to adults, and in fact will vary depending on age group across childhood. Additionally, children are managed in most EDs by a distinct team of clinicians using distinct protocols. As such, prehospital or triage-based sepsis prediction models applicable to adults are unlikely to work for children <18 years. Due to the above issues, implementation of a single sepsis care protocol for individuals age <18 years and age ≥18 years would impair the efficacy, feasibility, and generalizability of the proposed Code Sepsis protocol. Trauma patients are excluded because clinical identification of these patients is straightforward and triggers preexisting team-based care protocols with options for prehospital activation.

#### 4.2.5 Study phase dates

ED patients arriving to study EDs will be assigned to a study phase based on their ED arrival date.

- *Phase #1* (pre-intervention analysis phase): November 13, 2018 to November 12, 2019
- *Phase #2* (intervention roll-in): November 13, 2019 to February 12, 2020
- *Phase #3* (full intervention analysis phase): February 13, 2020 to February 12, 2021

#### 4.3 Waivers of Informed Consent and HIPAA authorization

This study comparing standard care to a new form of standard care will be carried out under a waiver of informed consent and HIPAA authorization (see section 9).

